#### 7.3.3 Expectedness Assessment

EXPECTED	Any AE or SAE for which the nature or severity is consistent with information in the Investigator Brochure
UNEXPECTED	Any AE or SAE for which the nature or severity is not consis- tent with information in the Investigator Brochure

### 7.4 Reporting Responsibilities of the Sponsor (DCC)

### 7.4.1 Sponsor Reporting Requirements to the Executive Committee, NHLBI and DSMB

The DCC-PI will notify the Executive Committee, NHLBI and DSMB of the occurrence of any death or unexpected and associated SAE (i.e. associated with the study product or study procedures) within 72 hours of the DCC receiving notification of the event. This will be followed by a written report no later than seven days after the DCC's initial notification of the event's occurrence. For all other SAEs, the DCC-PI will notify the Executive Committee, NHLBI, and DSMB no later than 15 days of the DCC receiving notification of the event. This will be followed by a written report no later than 30 days after the DCC's initial notification of the event. This will be followed by a written report no later than 30 days after the DCC's initial notification of the event's occurrence. The timing and contents of these reports are governed by the CCTRN *Guidelines for Reporting to Data Safety and Monitoring Board (DSMB)*.

### 7.4.2 Sponsor Reporting Requirements to FDA

Once the DCC has been notified of a SAE the following are the DCC's reporting requirements to the FDA:

- Fatal or life-threatening, unexpected SAE's and associated with the study drug must be reported to the FDA within 7 calendar days
- Other SAE's that are non-fatal or life-threatening, but are unexpected and associated with the study drug use must reported to the FDA with 15 calendar days

These 7-day and 15-day reports can be satisfied by completion of the FDA From 3500A (MedWatch Form), as well as any source documents as they relate to the event.

### 7.5 Unanticipated Problems (UPs)

An UP is an incident, experience, or outcome that specifically causes increased risk to the study or to its participants which may be of medical or non-medical etiology, and meets the following criteria:

• Unexpected (in terms of nature, severity, or frequency), given (a) the research procedures that are described in the protocol-related documents, such as the

IRB-approved research protocol and informed consent document; and (b) the characteristics of the subject population being studied;

- Definitely, probably or possibly related to participation in the research (i.e., there is a reasonable possibility that the incident, experience, or outcome may have been caused by the procedures or materials involved in the research); and
- Suggests that the research places patients or others at a greater risk of harm (including physical, psychological, economic, or social harm) than was previously known or recognized.

All UP reporting will follow the same guidelines as noted above for SAE reporting, and must include a corrective action plan/measures to prevent recurrence.

### 7.6 Guidelines for Holding Product in the Event of a Catheterization Facility Event

The events listed below will follow the same reporting criteria for SAE's as it relates to the investigational sites as well as the DCC:

- 1) Hypotensive episode
- 2) Hemodynamically significant arrhythmia requiring antiarrhythmic therapy
- 3) Hemodynamically unstable
- 4) Fever (Temperature increase to  $\geq 100.4^{\circ}$ F)
- 5) Excessive bleeding from bone marrow harvest site
- 6) Cardiac perforation

### 7.7 Monitoring of Liver Function Tests (AST/ALT)

Subjects with an AST and/or ALT elevation >1.5 x ULN are permitted to continue in the study but are required to have a serum liver function test panel drawn at the earliest possible date to reconfirm the elevated value and to be monitored approximately every 2 weeks thereafter until elevated liver enzyme value(s) resolved or returned to Baseline values, whichever occurred sooner.

### **8.0 ENDPOINT EVALUATION AND CLASSIFICATION**

A cardiac MR 1.5 T scanning unit (Avanto, Cardiac MR Scanner, Siemens Medical Systems or equivalent) will be used for cardiac MR images. The exact cMRI Scanner will vary at each institution, however, the exact imaging protocols will be established by the MRI Core Lab. cMRI was chosen by the Network to evaluate the primary and secondary endpoints because it is independent of the geometric assumptions required for calculations of ejection fraction compared to echocardiography or left-ventriculography. Furthermore, the inter-study reproducibility for cMRI is significantly better than echocardiography for measurements such as LVEF, LVEDV, LVESV and cardiac mass (36, 37). However, the patient's measurements of global LVEF from entry into the study until

completion will be assessed by echocardiography in place of cMRI when MRI is contraindicated.

A series of scout images will be required with a pulse sequence that collects an image in a fraction of the RR interval. Scout imaging will start with a transverse view at the mid-ventricular level. Using the first scout as a localizer, the technologist will acquire the next scout image for the image plane that intersects with the long axis of the LV. A horizontal long axis cine series (four chamber view) will be acquired first followed by the long axis cine (twp chamber view). The image planes for the short axis studies will start at the base of the heart, at least two cm above the mitral-tricuspid valve plane to achieve maximal LV coverage. Using Tru-FISP (balanced- FFE) cineangiography, the slices will be consecutively positioned every 7 mm from the base to apex with a 3 mm interslice gap. The acquisition window for retrospectively-triggered cine sequence will be obtained. End-expiratory breath-hold with sampling throughout the entire cardiac cycle will be employed because of better reproducibility of each slice position for more accurate left ventricular volume analysis. A minimum of 20 cardiac phases will be used to cover the RR interval. All patients will undergo baseline cMRI measurements at Day 3 given that resolution of myocardial stunning and improvement in global and regional LV function often continues to occur between Day 3 and Day 7 which would negatively bias the Day 7 group when LV function is reanalyzed at six months.

### 8.1 Functional Data Analysis

Commercial Siemens Argus analysis software will be used for measurement of global left myocardial mass, volumes, and ejection fraction. Short axis cine images will be placed in the 17 segment model (38) and a five point scale will be applied for a qualitative assessment of regional function. Segmental functional recovery will be measured in the defined infarct zone and each contiguous segment (border zone) and will be defined as an increase from akinetic to hypokinetic or normal; hypokinetic to normal; or dyskinetic to akinetic, hypokinetic or normal (4). Endocardial and epicardial borders will be traced in the short-axis slices in end-diastolic and end-systolic views for determination of LVEDV, LVESV and global LV mass. Global LVEF is calculated as (LVEDV-LVESV) / LVEDV x 100%. These measurements will also be reported on a normalized scale for body surface area (m^2 BSA). Regional systolic wall motion in the infarct and border zones will be expressed in mm of radial displacement of the endocardial contour. Regional wall thickening is defined as the percent increase of LV wall thickness during systole compared to diastole (18). The infarct zone will be defined as any myocardial seqment that demonstrates late enhancement with gadolinium. The border zone will be defined as all normal segments immediately adjacent to the infarct region.

### 8.2 Myocardial Infarction (MI) Data

Infarct size will be quantified by delayed, contrast enhanced MR imaging, which currently represents the most accurate method of assessment. Following left ventricular function assessment, gadolinium will be given using a 0.2 mmol/kg dose. Two minutes after gadolinium administration, single shot Tru-FISP short axis images will cover the LV in two to three breath-holds for evaluation of MVO. The TI of this sequence will be set to the lengthy value of 450 ms (in order to make normally perfused myocardium gray and areas of MVO black). After 20 minutes, the presence of hyperenhancement will be evaluated with diastolic 2D flash imaging. The TI will be adjusted to "null" normal myocardium. The entire LV will be covered following multiple breath holds using a slice thickness of 5 mm (to minimize partial volume averaging) and no interslice gap. The transmural extent of late hyperenhancement (infarct) will be defined as: 0-25%, 26-50%, 51-75% and >75%.

### 8.3 Myocardial Mass and Microvascular Obstruction (MVO) Data Analysis

The flash protocol for assessment of hyperenhancement will be used and myocardial mass will be planimetered using the Siemens *Argus* analysis software. A second analysis will planimeter only the areas of hyperenhancement on each 2D slice. The total mass of hyperenhanced tissue will then be reported as a percentage of the entire myocardial mass or the percentage of myocardium infarcted. MVO is manually calculated as the hypoenhanced region within the delayed hyperenhanced infarct region.

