Abbreviations: AMI, acute myocardial infraction; BMC, bone marrow cell; BMMNC, bone marrow mononuclear cell; CPC, circulating progenitor cell; EPC, endothelial progenitor cells; IC, intracoronary injection; ICM, ischemic cardiomyopathy; IM, intramyocardial infection using electromechanical mapping system; MI, myocardial infarction; MSC, mesenchymal stem cell; NR, not reported; OMI, old myocardial infraction; PBSC, peripheral blood stem cells; PCI, percutaneous coronary intervention; RCT, randomized controlled trial.

\*Values are given as mean ± SD unless otherwise

specified.

(See Appendix 1 for detailed description of major trials). A meta-analysis of 18 trials of cell therapy (including those using BMMNC, mesenchymal stem cells (MSC) and endothelial progenitor cells (EPC)) following AMI and in chronic ischemia in 999 patients was recently completed by Abdel-Latif et al. (13). They observed that on average, cell therapy significantly improved left-ventricular ejection fraction (LVEF) by 3.7%, reduced infarct size by 5.5% and decreased left-ventricular end-diastolic volume (LVEDV) by 4.8 ml. Their review supported the overall safety profile of cell therapy and suggested that the greatest improvement in LV function occurred when cells were administered 5-30 days following MI. They also observed that there was no significant difference in outcome in those patients that received less than the median number of cells compared to those who received greater than the median number of cells; however, dose effect has never been studied directly.

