## 2.1.3.6 Importance of microvascular obstruction (MVO)

Another critical factor is MVO as detected by cardiac magnetic resonance imaging (cMRI) (30, 31). MVO increases with ischemic duration (32) and frequently arises fol-

lowing PTCA revascularization during AMI as the result of embolization of thrombus, deposition of platelet-fibrin clot and endothelial cell sloughing within intramyocardial capillaries as a result of reperfusion injury (33). This is frequently manifested as reduced thrombolysis in myocardial infarction (TIMI) flow on the angiogram and portends a poor prognosis as it is associated with adverse left-ventricular remodeling and increased cardiovascular events (30).

The observation of TIMI 3 flow following revascularization for an AMI does not preclude the presence of significant MVO. In 110 patients with AMI and PTCA revacularization, MVO was observed in 46% of patients, yet 85% of patients had TIMI 3 flow (31). The presence of MVO in patients receiving intracoronary stem cells may impair BMMNC delivery to the areas of myocardium in greatest need of the therapy. Because MVO resolves over several weeks, the administration of stem cells at a very early period post-MI when MVO is at its peak may impair microvascular delivery to the myocardium. This may have contributed to the negative findings of Janssens et al. (16) who delivered BMMNC one day following MI. Indeed, a subgroup analysis by them demonstrated that the presence of significant MVO precluded significant recovery with cell therapy. Those patients without significant MVO statistically improved their LVEF by 5.5%. In contrast, the REPAIR-AMI Investigators noted in a subgroup analysis that those patients who received BMMNC five to seven days post-MI had a greater improvement in LVEF compared to those transplanted at an earlier time point when MVO may have been increased. We will carefully examine the role that MVO may play in intracoronary cell delivery in this study by its measurement at three and seven days by cMRI and correlation with outcomes.

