#### 2.2.1.1 Preliminary Results

Forty patients (31M, 9F) with moderate to large anterior infarctions have enrolled in the trial to date. Their average age is 54 years and seven have non-insulin dependent diabetes mellitus (NIDDM). Their average ischemic time is 7.2 hrs and seven have required intra-aortic balloon pump (IABP) support. Two patients underwent hypothermia treatment following initial cardiac arrest. The average day of transplant was five ± two days following their MI. The peak creatine kinase (CK) was 3074 IU and the CKMB was 282 IU. Their average LVEF by echocardiography performed one day following their MI was 37%. Their average LVEF by cMRI was 48% performed three to five days following their MI. In the Minneapolis Heart Institute, the LVEF by cMRI is 10% higher than that measured by echocardiography. All patients had significant MVO on their baseline MRIs. Their average LVEDV was 189.5 ml and left ventricular end systolic volume (LVESV) was 102.9 ml with an initial LV mass of 173 grams.

The average bone marrow aspirate collection was 65 ml and the mean BMMNC number was 170 million cells. The average percent  $CD34^+$ ,  $CD133^+$  and  $CD34^+/CD133^+$  cell TNC count in the delivered cell product was 2.01%, 0.22% and 1.09% respectively. The viability of the isolated BMMNC was greater than 96% in all patients.

Four significant adverse events were reported during the trial. One patient in the placebo group received an ICD for palpitations and syncope. One patient in the BMC group underwent CABG 8 months following cell therapy for an anomalous right coronary artery that was found to course between the aorta and pulmonary artery. One patient in the placebo group underwent repeat stenting in the LAD for in-stent restenosis at 15 months followed by CABG one month later after admission for a NSTEMI due to stent thrombosis. One patient in the BMC group underwent stenting of the circumflex artery two months following cell therapy infusion due to a pre-existing stenosis. There were no serious, unexpected, events that were related or possibly related to the study product or procedure reported during the trial.

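### Section 8.3 counts only hyperenhanced tissue as infarct, so the dark MVO core is left out at baseline and the change in infarct size is shifted toward apparent growth

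*Protocol*

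**What the plan says.** Protocol section 8.3 first planimeters the whole myocardium and then adds a step: "A second analysis will planimeter only the areas of hyperenhancement on each 2D slice". The result becomes the infarct-size measure: "The total mass of hyperenhanced tissue will then be reported as a percentage of the entire myocardial mass or the percentage of myocardium infarcted". The section closes with the definition of MVO: "MVO is manually calculated as the hypoenhanced region within the delayed hyperenhanced infarct region". Section 8.2 uses the same equation of infarct with enhancement: "The transmural extent of late hyperenhancement (infarct) will be defined as", followed by the transmurality bands. No section says that the hypoenhanced region is added to infarct mass.

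On frequency, section 2.2.1.1 reports of the 40-patient pilot that "All patients had significant MVO on their baseline MRIs". Section 2.1.3.6 reports MVO in 46% of a cited cohort of 110 patients. On time course, section 2.1.3.6 reasons from the premise "Because MVO resolves over several weeks".

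Infarct size is a secondary endpoint, analysed as change from baseline to six months (section 1.2), for both the cell effect and the timing effect (sections 3.2.3 and 9.4.3).

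**The concern.** MVO lies inside the infarct by the protocol's own definition, yet it is dark, and only bright tissue is planimetered. Followed as written, the rule leaves out part of the infarct at the early scan. By six months MVO has resolved on the protocol's account, so the same tissue can no longer be missing for that reason. The two visits then measure different tissue, and a patient whose infarct has not changed would appear to show growth.

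Three results are exposed. Within-arm changes in infarct size would be misread. The planned examination of MVO against outcomes (section 2.1.3.6) would correlate MVO with a change score that already contains it. The timing comparison could also be distorted if the two timing arms take their baselines on different days, because the amount of MVO left out could then differ between them.

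**Working it through.** **No stated figure to reproduce.** The protocol gives no power, standard deviation or MVO mass for infarct size. The check is algebra, with a range of assumed values.

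**Inputs from the protocol.** MVO prevalence *p* = 0.46 (section 2.1.3.6) or 1.00 (section 2.2.1.1). Arms of 40 and 40 active, 20 and 20 placebo (section 3.2.6). The timing contrast is active Day 7 against active Day 3 (section 3.2.6.2).

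**Assumptions not in the protocol.** Mean MVO core *m* = 3 to 8% of LV mass among patients who have MVO; SD of true change 8 points; true cell effect −5.5 points; share of MVO gone by Day 7, *r* = 0 to 0.5; resolved core enhances as scar by six months.

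**Step 1: one patient.** Let I0 and I6 be true infarct size and M the dark core at baseline.
- Measured baseline = I0 − M
- Measured month 6 = I6
- Measured change = (I6 − I0) + M

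The error equals the baseline core and always points toward growth.

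**Step 2: within-arm mean.** Shift = *p* × *m*.

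| Prevalence | Core 3% | Core 8% |
|---|---|---|
| 0.46 | 0.46 × 3 = 1.4 points | 0.46 × 8 = 3.7 points |
| 1.00 | 3.0 points | 8.0 points |

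**Step 3: cells versus placebo.** M is fixed before infusion, so its expectation is the same in both therapy arms and it cancels in the difference. A simulation with the protocol's arm sizes (core SD set at half its mean, truncated at zero, independent of true change) returned an effect of −5.5, to within simulation error, in every scenario. The standard error rose from 1.56 with no MVO to at most 1.80. In that worst case the relative efficiency is (1.56/1.80)² = 0.75.

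**Step 4: MVO against infarct-size change.** Cov(measured change, M) = Cov(true change, M) + Var(M). The second term is positive whenever MVO varies between patients, so MVO is tied to apparent growth even if it has no relation to true change.

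**Step 5: active Day 7 versus active Day 3.** If each arm uses its own pre-infusion scan, the omitted core is M on Day 3 and (1 − *r*)M on Day 7. Bias = −*r* × *p* × *m*.
- Smallest non-zero case: 0.25 × 0.46 × 3 = 0.35, so about −0.4 (simulated −0.36)
- Largest: 0.50 × 1.00 × 8 = 4.0, so −4.0 (simulated −4.03)
- If *r* = 0, or if both arms use the Day 3 scan: 0

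The sign favours Day 7. A placebo-corrected interaction had bias of about 0, but section 3.2.6.2 describes the active-only contrast.

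**Step 6: which baseline applies?** Section 8.0 has every patient's baseline cMRI on Day 3, so that recovery between Day 3 and Day 7 does not penalise the Day 7 group. Section 9.4.2 compares month 6 with the Day 3 scan in one arm and the Day 7 scan in the other. Section 9.4.3 repeats the pre-infusion baseline for the secondary endpoints but names LVEF as the analysis variable, so it does not settle the matter for infarct size. The condition for the bias in step 5 is therefore left open.

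**The case against.** The word *only* in section 8.3 can be read as a contrast with the whole-myocardium planimetry in the sentence before it, and the closing sentence describes an infarct region that contains the dark core. Nothing tells readers to subtract that core, and a core-laboratory manual, not shown here, may add it back. This stands in part: exclusion is the literal reading, not an explicit instruction to omit. The text still makes hyperenhanced mass the reported infarct percentage, and two readers could contour the same scan differently.

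The frequency is uncertain. The pilot enrolled LAD infarcts only, while TIME accepts any infarct artery of at least 2.5 mm, and the cited cohort shows 46%. Section 8.2 images MVO at two minutes and hyperenhancement at 20 minutes; only a core still dark on the later images affects the planimetry, and section 2.2.1.1 does not say which images its statement rests on. This stands: under-measurement in most patients cannot be asserted. That the resolved core enhances at six months is also an inference from MVO lying within the infarct; the protocol does not state it.

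A reader might infer that the infarct-size endpoint as a whole is invalid. Step 3 does not support that: the randomised cell contrast is unbiased in expectation. A reader might also set the shift beside the meta-analysis result in section 2.1.2, which "reduced infarct size by 5.5"%. That is a treatment effect, whereas the shift is common to both therapy arms and cancels between them; nor does the section say whether the figure is absolute or relative.

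A fixed loss of precision cannot be claimed either. With an assumed MVO SD of 4 and a true-change SD of 6 to 8, independence gives √(36 + 16) = 7.2 to √(64 + 16) = 8.9, a loss of 1 − 36/52 = 31% to 1 − 64/80 = 20%. If larger cores go with more shrinkage, the loss disappears at a correlation of −4/(2 × 6) = −0.33 or −4/(2 × 8) = −0.25. Covariate adjustment under section 9.4.3 could also recover some of it.

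Finally, the scope is narrow. Infarct size is one of five listed secondary endpoints and is absent from the listed secondary hypotheses. Global LVEF and the segment-based infarct zone of section 8.1 do not depend on this planimetry.

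**Conclusion.** The measurement rule in section 8.3 is wrong as written for a change endpoint. It leaves out tissue that the same section places inside the infarct, at the visit where that tissue is most likely to be dark. Wherever MVO persists on the delayed baseline images, infarct size is under-measured, and change to six months moves toward apparent growth by about the baseline MVO mass. The average shift is about 1.4 to 8 points of LV mass on the assumed core of 3 to 8% and the two prevalences in the protocol; the documents themselves cannot fix it.

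The consequences differ by analysis. Cells versus placebo is unbiased in expectation, with a possible loss of precision. Within-arm changes, and analyses relating MVO to infarct-size change, carry a built-in artefact. Active Day 7 versus active Day 3 could be biased by about 0.4 to 4 points in favour of Day 7, but only if the arms use different baseline days and 25 to 50% of the MVO has gone by Day 7, which is an assumption. Neither co-primary endpoint is shown to be affected.

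**What to change.** In section 8.3, state that infarct mass at every visit is the hyperenhanced area plus the hypoenhanced (MVO) region within the infarct, that this total is used for the infarct-size endpoint, and that MVO mass is also reported separately. Carry the same rule into any core-laboratory reading instructions.

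Reconcile section 8.0 with sections 9.4.2 and 9.4.3 by naming the baseline scan that applies to infarct size, and correct the analysis variable in section 9.4.3, which names LVEF.

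The cost is a few sentences. MVO is already delineated by hand, and under section 6.3 every patient has a Day 3 scan and the Day 7 group a repeat on Day 7. No new scan, visit or patient is needed. Images already read under the literal rule would need the MVO region added to the infarct total.
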